### **3.5.7.6 Follow-up of Adverse Events**

All AEs must be reported in detail on the appropriate page of the eCRF and followed until the AE is resolved or stable or judged by the investigator to be not clinically significant in Part A of the study. For Part B of the study, only AESIs and SAEs will be recorded. The investigator may request an unscheduled visit at any time, if warranted.

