## 1 Introduction

### 1.1 Background

Zika virus (ZikaV) is a single-stranded RNA flavivirus, which is transmitted to humans by a mosquito vector (mainly *Aedes aegypti* but other *Aedes* mosquitoes are believed to be competent vectors) or by person-to-person spread, mainly through sexual transmission. ZikaV has been found in blood and other body fluids (saliva, urine, semen) in which it can persist longer than in the blood ([Franca et al 2016](#)). Due to the common vector, ZikaV has a similar epidemiology and transmission cycle to chikungunya and dengue. Most infections are either asymptomatic or result in a mild febrile illness with a rash. However, infection with ZikaV is also causally associated with Guillain-Barré syndrome neuropathy and other neurological sequelae in infected adults as well as congenital malformation of the brain (eg, microcephaly, ventricular calcifications) and other severe impairments (eg, intrauterine growth restriction) in infants born to mothers infected early in the pregnancy ([Brasil et al 2016](#)).

Currently there is no vaccine to protect against this disease, which has spread rapidly from Asia to most tropical and subtropical regions including the Americas. The Centers for Disease Control and Prevention (CDC) has listed ZikaV as a Level 1 alert ([Bramm 2016](#)). The World Health Organization (WHO) has declared ZikaV to be a global public health emergency and has initiated a strategic framework to aid in rapid response ([WHO, 2016a](#)).

Moderna Therapeutics, Inc. has developed a proprietary messenger RNA (mRNA)-based vaccine platform. This is based on the principle and observations that antigens can be produced in vivo by delivery and uptake of the corresponding mRNA by cells. The mRNA then undergoes intracellular ribosomal translation to endogenously express the protein antigen(s) encoded by the vaccine mRNA. This mRNA-based vaccine does not enter the cellular nucleus or interact with the genome, is non-replicating, and expression is transient. mRNA vaccines thereby offer a mechanism to stimulate endogenous production of structurally intact protein antigens in a way that mimics wild type viral infection and is able to induce highly targeted immune responses against infectious pathogens such as ZikaV.

mRNA-1325 is an mRNA-based vaccine candidate being tested for its ability to safely induce an immune response with the intention to be able to prevent ZikaV infection.

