### **3.2.2 Exclusion Criteria**

Subjects meeting any of the following criteria will be excluded from the study:

1. The subject has any ongoing significant chronic illness requiring medical or surgical care. Asymptomatic conditions or findings (eg, mild hypertension, dyslipidemia) that are not associated with evidence of end-organ damage are not exclusionary provided that they are being appropriately managed and are clinically stable in the opinion of the investigator (ie, unlikely to result in symptomatic illness within the time-course of this study).
2. The subject has a history of active cancer (malignancy) in the last 10 years (exception is subjects with adequately treated non-melanomatous skin carcinoma, who may participate in the study).
3. The subject is a female of childbearing potential and has a positive pregnancy test at Screening or on the day of vaccination.
4. The subject has abnormal liver enzyme tests (increase in aspartate aminotransferase, alanine aminotransferase, or alkaline phosphatase) at Screening.
5. The subject has received another investigational product in another investigational study within 60 days, or 5 half-lives, whichever is longer, before the planned date of first vaccination.
6. The subject has received any live attenuated vaccines within 4 weeks before enrollment or inactive vaccines within 2 weeks before enrollment, or plans to receive any vaccine during the active vaccination period (through 4 weeks after their last planned vaccination).
7. The subject has received (at any time) a vaccine for Zika or dengue vaccine.
8. The subject has a history of confirmed Zika or dengue infection.
9. The subject has lived in or visited any Zika-endemic area (as defined by WHO; [Appendix 4](#)) greater than 4 weeks in duration (flavivirus-seronegative group, only).
10. The subject has received any vaccination for a flavivirus (eg, yellow fever, Japanese encephalitis) in his or her lifetime (flavivirus-seronegative group, only), or received a vaccination for a flavivirus more than 20 years ago (flavivirus-seropositive group, only).

11. The subject has a positive West Nile virus antibody titer above the detection level of the assay (flavivirus-seronegative group, only). NOTE: West Nile virus titers are considered valid for a period of 90 days (allowing for the screening period on West Nile virus to exceed the standard 28 days as noted for all other screening parameters).

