### **3.5.1 Safety Contact**

Once entered into Part B, each safety contact will occur by telemedicine (eg, telephone, text message, internet), and blood samples for immune persistence will be collected from each subject at the time points indicated in [Table 6-2](#).

Safety contacts must be performed by appropriately trained study site staff. If the initial contact is unsuccessful, the study site staff should make a total of 3 attempts for each scheduled safety contact. All attempts to contact the subjects will be recorded in the source documents. The safety contact is considered missed if there is a failure to contact the subject by the time of the succeeding visit (every 28 days plus window allowance).

These contacts will follow a script, which will facilitate the collection of relevant safety information. Each safety contact will capture outcomes of any AESI or SAE that remains unresolved since the last visit or is newly identified through scripted query. Additional data may be requested through medically attended visits, and medications and vaccination will be recorded as part of the medical intake for each telemedicine visit. All safety information

described by the subject must be documented in the source documents and not documented on the script used for the safety contact.

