### **3.5.7.2 Eliciting and Documenting Adverse Events**

The investigator is responsible for ensuring that all AEs and SAEs are recorded in the eCRF and reported to Moderna Therapeutics, Inc. In Part A of the study, AEs will be assessed from the time of the first dose administration at Visit 1 through Visit 7. However, for the time period after the ICF is signed until before receiving the study drug, AEs will only be recorded when they are defined as one or more of the following: SAEs, AESIs, or AEs leading to study withdrawal. In Part B of the study, AESIs and SAEs will be assessed from Visit 8 through Visit 19. Any AEs occurring before receipt of the study drug will be analyzed separately from TEAEs.

At every clinic visit or telephone contact, subjects will be asked a standard question to elicit any medically related changes in their well-being according to the scripts provided. Subjects will also be asked if they have been hospitalized, had any accidents, used any new medications, or changed concomitant medication regimens (both prescription and over-the-counter medications).

In addition to subject observations, data from clinical laboratory test results, physical examination findings, or other documents relevant to subject safety classified as an AE will be documented on the AE page of the eCRF.

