#### 3.6.5.1 Immunogenicity Analyses

The following immunogenicity outcome measures (for serum neutralizing antibody titers) and their 95% CIs, where appropriate, will be summarized by treatment group and by visits after each vaccination:

- Geometric mean titer (GMT) of anti-Zika virus neutralizing antibodies (PRNT50 assay)
  - Part A: At Baseline (pre-vaccination at Visit 1) and on 28 days after both first and second vaccination (Visits 4 and 7, respectively)
  - Part B: At 168 ( $\pm 15$ ) days and 364 ( $+15$ ) days (Visits 12 and 19, respectively) will be evaluated if interim immunogenicity analyses warrants long term analyses of persistence.
- Geometric mean ratio (GMR)Post/Pre
  - Part A and Part B: The ratio of post-vaccination GMT to pre-vaccination (Visit 1) GMT of subjects who have a baseline sample (pre-vaccination at Visit 1) and post-vaccination sample at any post-dose time point (Visits 4, 7, 12, or 19; data from visits 12 and 19 will be included only if based on interim immunogenicity analyses results the evaluation of these later timepoints is warranted.)
- Seroconversion

- Part A: The proportion of subjects with Zika virus PRNT50 titer  $\geq 1:10$ ,  $\geq 1:20$ ,  $\geq 1:40$ ,  $\geq 1:80$ ,  $\geq 1:160$ , and  $\geq 1:320$  at Baseline, Visit 4, and Visit 7
- Part A: The proportion of subjects with baseline Zika virus PRNT50 titer  $< 1:10$  and post-vaccination Zika virus PRNT50 titer of  $\geq 1:20$ ; or with baseline Zika virus PRNT50 titer  $\geq 1:10$  and with post-vaccination 4-fold titer increase (Visits 4 or 7)
- Part B: The proportion of subjects who maintained seroconversion status at specific time points of 168 ( $\pm 15$ ) days and 364 ( $+15$ ) days (Visits 12 and 19, respectively). Data from visits 12 and 19 will be included only if based on interim immunogenicity analyses results the evaluation of these later timepoints is warranted.
- Cross-Stimulation with prior flavivirus vaccination (subset of flavivirus-seropositive subjects)
  - Part A:
    - Geometric mean titer (GMT) of anti-yellow fever neutralizing antibodies at Baseline, Visit 4, and Visit 7
    - Geometric mean ratio (Post/Pre) of anti-yellow fever neutralizing antibodies at Visit 4 and Visit 7
    - The proportion of subjects with anti-yellow fever antibody titer  $\geq 1:10$ ,  $\geq 1:20$ ,  $\geq 1:40$ ,  $\geq 1:80$ ,  $\geq 1:160$ , and  $\geq 1:320$  at Baseline, Visit 4, and Visit 7

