**Table 1. Countries and territories that have reported mosquito-borne Zika virus transmission**

Classification	WHO Regional Office	Country / territory	Total
Category 1: Countries with a reported outbreak from 2015 onwards #	AFRO	Angola; Cabo Verde; Guinea-Bissau	3
	AMRO/PAHO	Anguilla; Antigua and Barbuda; Argentina; Aruba; Bahamas; Barbados; Belize; Bolivia (Plurinational State of); Bonaire, Sint Eustatius and Saba – Netherlands; Brazil; British Virgin Islands; Cayman Islands; Colombia; Costa Rica; Cuba; Curaçao; Dominica; Dominican Republic; Ecuador; El Salvador; French Guiana; Grenada; Guadeloupe; Guatemala; Guyana; Haiti; Honduras; Jamaica; Martinique; Mexico; Montserrat; Nicaragua; Panama; Paraguay; Peru; Puerto Rico; Saint Barthélemy; Saint Kitts and Nevis; Saint Lucia; Saint Martin; Saint Vincent and the Grenadines; Sint Maarten; Suriname; Trinidad and Tobago; Turks and Caicos; United States of America; United States Virgin Islands; Venezuela (Bolivarian Republic of)	48
	WPRO	American Samoa; Fiji; Marshall Islands; Micronesia (Federated States of); Palau; Samoa; Singapore; Tonga	8
Subtotal			59
Category 2: Countries with possible endemic transmission or evidence of local mosquito-borne Zika infections in 2016 or 2017	SEARO	Indonesia; Maldives; Thailand	3
	WPRO	Malaysia; New Caledonia; Philippines; Viet Nam	4
Subtotal			7
Category 3: Countries with evidence of local mosquito-borne Zika infections in or before 2015, but without documentation of cases in 2016 or 2017, or outbreak terminated	AFRO	Gabon**	1
	PAHO/AMRO	ISLA DE PASCUA – Chile**	1
	SEARO	Bangladesh**	1
	WPRO	Cambodia**; Cook Islands**; French Polynesia**; Lao People's Democratic Republic; Papua New Guinea; Solomon Islands; Vanuatu	7
Subtotal			10
Total			76

PPD will operationalize the monitoring of the Zika-endemic changes and notify a site if they appear to be reaching the endemic listing.

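### Part B records neither non-serious flavivirus infection nor travel, so a titer raised by natural infection could be reported as persistence of the mRNA-1325 response

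*Protocol*

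**What the plan says.** **Event capture.** Protocol 3.5.7.6 states: "For Part B of the study, only AESIs and SAEs will be recorded". Section 3.5.7.2 applies the same limit to Visits 8 to 19. Table 6-2 schedules safety contacts, two blood draws, AESIs, SAEs, selected concomitant medications and the end-of-study visit. It has no line for infection or travel. The AESI list in Appendix 2 covers immune-mediated disease and contains no flavivirus infection.

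**Expected course of infection.** Section 1.1 says of Zika: "Most infections are either asymptomatic or result in a mild febrile illness with a rash".

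**What each contact asks.** Under 3.5.7.2, "subjects will be asked a standard question to elicit any medically related changes in their well-being according to the scripts provided". Section 3.5.1 requires that safety information "described by the subject must be documented in the source documents and not documented on the script used for the safety contact".

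**Exposure control.** Exclusion criterion 9 ("The subject has lived in or visited any Zika-endemic area", for more than 4 weeks) applies at entry and only to the seronegative group. After entry, Appendix 4 provides only that the contract research organisation will "notify a site if they appear to be reaching the endemic listing".

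**Vaccines.** Criterion 6 excludes a subject who "plans to receive any vaccine during the active vaccination period (through 4 weeks after their last planned vaccination"). After that period other vaccines are not barred, but section 3.4.8.2 and Table 6-2 collect them through Visit 19.

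**Endpoint.** Section 3.6.5.1 reports GMT and GMR at Visits 12 and 19, and "The proportion of subjects who maintained seroconversion status at specific time points". These are evaluated only if interim immunogenicity results warrant it.

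**The concern.** The Visit 12 and 19 titers are meant to show how long the vaccine response lasts. An infection after Visit 7 can raise a subject's Zika titer independently of the vaccine, and that subject would then score as having maintained seroconversion. The error runs in one direction, towards apparent durability.

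The protocol treats prior flavivirus exposure as a confounder at screening. It excludes past Zika or dengue infection in everyone and, in the seronegative group, a positive West Nile titer, any flavivirus vaccination and long stays in Zika areas. After entry, only vaccination is still followed at subject level.

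Exposure is not remote. Sites may be in the United States or its territories, and the Appendix 4 table lists the United States, Puerto Rico, the US Virgin Islands and American Samoa as having had outbreaks from 2015 onwards. Section 1.6 calls West Nile the most prevalent flavivirus infection in the United States. The seropositive group, recruited through military assignment or travel-type vaccination certificates, has no travel exclusion at all.

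**Working it through.** **Step 1: would any Part B record show the infection?**

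| Possible record | Catches a non-serious infection? |
|---|---|
| SAE | No, by definition |
| AESI | No; infection is not on the list |
| Concomitant medication | Only if an immune-affecting product was given |
| Well-being question | Perhaps if symptomatic; the answer goes to source documents, with no Part B event record |
| Travel | No scheduled item |
| Appendix 4 monitoring | Site level only |

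A symptomatic mild case could survive in source notes. An asymptomatic one would not appear anywhere.

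**Step 2: group sizes.** The protocol makes no formal sample size calculation, so there is no powered figure to reproduce. Its allocation does reproduce: 30 × 4/5 = 24 vaccine and 30 × 1/5 = 6 placebo per cohort; over three cohorts, 72 + 18 = 90. The planned two-thirds to one-third serostatus split, if it holds among vaccinees, gives 24 × 2/3 = 16 seronegative and 24 × 1/3 = 8 seropositive per dose.

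**Step 3: effect of one boosted subject on the GMT.** The LLOQ is not given; I assume 1:10. Section 3.6.6 then enters a value below LLOQ as 0.5 × 10 = 5. If one of n subjects moves from 5 to T, the GMT is multiplied by (T/5)^(1/n). For T = 320 the ratio is 64; for T = 1280 it is 256.

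| n | T = 320 | T = 1280 |
|---|---|---|
| 24 (whole dose group) | 64^(1/24) = 1.19 | 256^(1/24) = 1.26 |
| 16 (seronegative) | 64^(1/16) = 1.30 | 256^(1/16) = 1.41 |
| 8 (seropositive) | 64^(1/8) = 1.68 | 256^(1/8) = 2.00 |

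With T from 40 to 640 instead, the ranges are 1.09 to 1.22, 1.14 to 1.35 and 1.30 to 1.83. A subject who had not waned as far as 5 would move the mean less.

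**Step 4: effect on maintained seroconversion.** One subject who would otherwise have lost the status adds 1/24 = 4.2, 1/16 = 6.25 or 1/8 = 12.5 percentage points.

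**Step 5: would placebo reveal it?** The chance of at least one exposed subject among m is 1 − (1 − p)^m. The protocol gives no exposure rate, so p is assumed.

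| 12-month rate p | At least one among 24 vaccinees at a dose | At least one among 18 placebo |
|---|---|---|
| 1% | 21% | 17% |
| 2% | 38% | 30% |
| 5% | 71% | 60% |
| 10% | 92% | 85% |

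At 2%, the pooled placebo group shows no exposure at all about 70% of the time. Even when it shows one, it does not identify which vaccinees were boosted.

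**The case against.** **The SAP may settle it.** This is right for vaccines. A reader might infer that titers drawn after a yellow fever or Japanese encephalitis vaccine permitted in Part B are kept as persistence. The protocol does not say so. Vaccine receipt is collected through Visit 19 and summarised, so those subjects are identifiable, and the handling rule can sit in the SAP, which is not shown. The answer does not extend to infection and travel, because a SAP cannot analyse data that were not collected.

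**The script is not shown and could ask about travel.** That is possible, but neither Table 6-2 nor section 3.5.1 calls for it, and section 3.5.7.6 gives a non-serious illness no event record.

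**It might be repaired later.** A reader might conclude that the gap is irreparable. That is too strong. Source notes, consented access to medical records, exploratory sera at Visits 12 and 19, and optional assays for other flaviviruses all exist. None is set up as an infection marker, so the repair would be partial.

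**Cross-reactivity is assumed.** This stands in part. A Zika infection bears directly on the Zika titer. That dengue or West Nile infection would raise Zika PRNT50 is not stated in the protocol, whose own cross-stimulation analysis looks in the other direction, at yellow fever titers after mRNA-1325.

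**The endpoint is secondary and conditional.** This is also true. Safety is the primary objective, and the interim dose decisions use Part A data.

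**Conclusion.** The point holds as a gap in data collection. As written, Part B leaves no subject-level data record of non-serious flavivirus infection or travel, so a titer raised by natural infection could be reported as a lasting response to mRNA-1325.

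One boosted subject multiplies the GMT by about 1.19 to 1.26 in a whole dose group, 1.30 to 1.41 in about 16 seronegatives and 1.68 to 2.00 in about 8 seropositives. The same subject adds up to 4, 6 or 12.5 percentage points to maintained seroconversion. These figures rest on the assumed LLOQ, a response fully waned to 5 and the assumed post-exposure titers. The stratum figures matter because section 1.4 intends to compare immune responses by serostatus.

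A reader might infer that boosting will certainly be counted as persistence. The documents support only that it could be: an exposure must occur, and persistence testing must be triggered. Dose selection from Part A and the primary safety comparison are not affected.

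**What to change.** Add two items to the Part B script and eCRF at Visits 8 to 19:

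1. Any diagnosed or suspected flavivirus infection since the last contact, recorded with its date even if non-serious.
2. Travel since the last contact to a place with local Zika transmission, with dates. Define this below country level, or as travel away from the home area. The Appendix 4 table lists the United States itself, so an item on any stay in a listed country would flag nearly every subject.

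In section 3.6.5.1 or the SAP, specify that the Visit 12 and 19 Zika PRNT50 persistence summaries exclude values drawn after a recorded flavivirus infection or non-study flavivirus vaccination. The vaccine data for this are already collected. Add a supportive summary that also excludes values after such travel.

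The cost is two questions on calls already scheduled every 28 days, one eCRF page and one analysis rule. A few late values will drop out of the persistence summary, and the supportive summary will lose some travellers who were never infected. Asymptomatic infections without travel will still go undetected, so the change narrows the gap without closing it. The items must be in place before the decision to test persistence, because exposure history is best collected as it happens.

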### **3.5.8 Clinical Laboratory Testing**

Clinical laboratory tests will be performed by the central laboratory, unless specified otherwise. Blood and urine will be collected in Part A at the time points indicated in the schedule of events ([Table 6-1](#)). Fasting is not required before collection of laboratory samples.

The following hematology, serum chemistry, urinalysis, and other laboratory assessments will be performed. The results will be toxicity scored using [Table 6-4](#).

Hematology:	Hematocrit, hemoglobin, mean corpuscular hemoglobin, mean corpuscular hemoglobin concentration, mean corpuscular volume, platelet count, red blood cell count, and total and differential white blood cell count
Serum chemistry:	Alanine aminotransferase, alkaline phosphatase, aspartate aminotransferase, amylase, lipase, bilirubin (total and direct), blood urea nitrogen, creatinine, random glucose, potassium, sodium, total protein, albumin, and calcium
	Females subjects only: $\beta$ -human chorionic gonadotropin (childbearing potential) and follicle-stimulating hormone (post-menopausal)
Urinalysis:	pH, protein, glucose, ketone, bilirubin, urobilinogen, blood, nitrite, leucocytes, and specific gravity
Coagulation:	Prothrombin time and partial thromboplastin time

A pregnancy test ( $\beta$ -human chorionic gonadotropin) will be performed on all female subjects of childbearing potential at Screening (serum pregnancy test), before each dose administration (urine pregnancy test), and as needed at unscheduled visits (serum pregnancy test). Serum pregnancy tests will be sent to the central laboratory, while urine pregnancy tests will be performed by the local laboratory on site. A follicle-stimulating hormone test will be performed at Screening, as necessary, to confirm post-menopausal status in female subjects, if not documented in the subject's medical records.

Human immunodeficiency virus (types 1 or 2) antibody, hepatitis B surface antigen, and hepatitis C virus antibody will be assessed at Screening.

At Screening, if the subject has no proof of yellow fever vaccination within 20 years, or other documentation of flavivirus status, the West Nile virus screening test will be administered. A West Nile virus serology screen can occur up to 90 days prior to randomization.

A urine screen for drugs of abuse will be performed by the local laboratory at Screening and before dose administration at Visit 1 for opiates, cocaine, phencyclidine, amphetamines, benzodiazepines, and methadone (cannabis excluded).

Should safety laboratory testing at 7 days post-vaccination result in a Grade 2 or greater toxicity score, then repeat testing within the next 10 days must occur and this may include an unscheduled visit. Should the subject's laboratory test value not return to Baseline then periodic testing may be needed until the abnormality is deemed to be associated with a new stable AE or determined to be not clinically significant by the investigator.

Those values that fall within the normal range of the laboratory will automatically be classified as normal and receive a toxicity score of 0. All values that have a toxicity score of Grade 1 or greater will also be evaluated by the investigator and classified as “abnormal clinically significant (CS)”, or “abnormal not clinically significant (NCS).” Investigators should use their clinical judgment when considering the clinical significance of any abnormal laboratory findings. All laboratory test values with a toxicity score of Grade 3 or greater will be entered as AEs. Any additional laboratory test value that is determined to be clinically significant will also be recorded as an AE, should that be considered the primary diagnosis. In such instances, the abnormal value and grade will be documented on the AE page of the eCRF. The investigator will continue to monitor the subject with additional assessments until the values have reached the reference range or the values at Screening or until the investigator determines that follow-up is no longer medically necessary. The only exception to this rule would be a laboratory test value that is associated with an identified ongoing AE where that event would be the classifying AE.

